## 7 ADVERSE EVENT REPORTING

### 7.1 Adverse Events

An **Adverse Event (AE)** is defined as any new untoward medical occurrence or worsening of a pre-existing medical condition in a patient or clinical investigation subject administered an investigational (medicinal) product and that does not necessarily have a causal relationship with this treatment. An AE can therefore be any unfavorable and unintended sign (including an abnormal laboratory finding, for example), symptom, or disease temporally associated with the use of investigational product, whether or not considered related to the investigational product.

#### 7.1.1 Serious Adverse Events

A **Serious Adverse Event (SAE)** is any untoward medical occurrence that at any dose:

- results in death
- is life-threatening (defined as an event in which the subject was at risk of death at the time of the event; it does not refer to an event which hypothetically might have caused death if it were more severe)
- requires inpatient hospitalization or causes prolongation of existing hospitalization (see note below for exceptions)
- results in persistent or significant disability/incapacity
  - is a congenital anomaly/birth defect
  - is an important medical event (defined as a medical event(s) that may not be immediately life-threatening or result in death or hospitalization but, based upon appropriate medical and scientific judgment, may jeopardize the subject or may require intervention [eg, medical, surgical] to prevent one of the other serious outcomes listed in the definition above.) Examples of such events include, but are not limited to, intensive treatment in an emergency room or at home for allergic bronchospasm; blood dyscrasias or convulsions that do not result in hospitalization.) Potential drug induced liver injury (DILI) is also considered an important medical event. (See Section 6.6 for the definition of potential DILI.)

Suspected transmission of an infectious agent (eg, pathogenic or nonpathogenic) via the study drug is an SAE.

All pregnancies, regardless of outcome, must be reported to BMS, **including pregnancies that occur in the female partner of a male study subject. All pregnancies must be followed to outcome.** See Section 7.6 for instructions on reporting pregnancies.

Although pregnancy, overdose, cancer, and potential drug induced liver injury (DILI) are not always serious by regulatory definition, these events must be handled as SAEs and should also be reported to BMS in an expedited manner, as described in Section 7.2.

**NOTE:** The following hospitalizations are not considered SAEs in BMS clinical studies:

- a visit to the emergency room or other hospital department lasting less than 24 hours that does not result in admission (unless considered an “important medical event” or a life-threatening event) or administration of intravenous antibiotics
- elective surgery planned before signing consent
- admissions as per protocol for a planned medical/surgical procedure
- routine health assessment requiring admission or procedures for baseline/trending of health status (eg, routine colonoscopy)
- medical/surgical admission for purpose other than remedying ill health state that was planned before study entry. Appropriate documentation is required in these cases.
- admission encountered for another life circumstance that carries no bearing on health status and requires no medical/surgical intervention (eg, lack of housing, economic inadequacy, caregiver respite, family circumstances, administrative).

#### **7.1.2        *Nonserious Adverse Events***

Nonserious adverse events are all adverse events that are not classified as SAEs.

#### **7.2            *Assignment of Adverse Event Intensity and Relationship to Abatacept***

All adverse events, including those that are serious, will be graded by the investigator as follows:

- Mild (Grade 1): awareness of event but easily tolerated
- Moderate (Grade 2): discomfort enough to cause some interference with usual activity
- Severe (Grade 3): inability to carry out usual activity
- Very Severe (Grade 4): debilitating; significantly incapacitates subject despite symptomatic therapy.

The following categories and definitions of causal relationship to investigational product as determined by a physician should be used:

- **Related:** There is a reasonable causal relationship to investigational product administration and the adverse event.
- **Not Related:** There is not a reasonable causal relationship to investigational product administration and the adverse event.

The expression “reasonable causal relationship” is meant to convey in general that there are facts (eg, evidence such as de-challenge/re-challenge) or other arguments to suggest a positive causal relationship.

### **7.3 Collection and Reporting**

Adverse events can be spontaneously reported or elicited during open-ended questioning, examination, or evaluation of a subject. To prevent reporting bias, subjects should not be questioned regarding the specific occurrence of one or more adverse events.

If known, the diagnosis of the underlying illness or disorder should be recorded, rather than its individual symptoms. The following information should be captured for all AEs: onset, duration, intensity, seriousness, relationship to investigational product, action taken, and treatment required. If treatment for the event was administered, it should be recorded in the medical record. The investigator must supply BMS and the IRB/IEC with any additional information requested, notably for reported deaths of subjects.

Completion of supplemental CRFs may be requested for AEs and/or laboratory abnormalities that are reported/identified during the course of the study.

A data safety monitoring board (one to-be-named Rheumatology faculty member plus one to-be-named statistician) will review the SAEs quarterly and issue a report to the IRB and to the investigators regarding AEs and SAEs, reported according to patient assignments to groups A or B (the double-blind code will not be broken); these reports will also be supplied to the sponsor

#### **7.3.1 Serious Adverse Events**

Following the subject's written consent to participate in the study, all SAEs must be collected, including those thought to be associated with protocol-specified procedures. Collection of all SAEs must continue for 30 days after the last administration of the investigational product. If applicable, SAEs must be collected that relate to any later protocol-specified procedure. The investigator should notify BMS of any SAE occurring after this time period that is believed to be related to the investigational product or protocol-specified procedure.

All SAEs, whether considered related or unrelated to abatacept, must be reported to BMS (by the investigator or designee) within 24 hours of study personnel becoming aware of the event. If only limited information is initially available, follow-up reports are required. The original SAE form must be kept on file at the study site.

All SAEs should be faxed or emailed to BMS at:

**Global Pharmacovigilance & Epidemiology  
Bristol-Myers Squibb Company  
[contact]  
Email: [contact]**

For studies conducted under an **Investigator IND**, any event that is both serious and unexpected must be reported to the Food and Drug Administration (FDA) as soon as possible **and no later than 7 days** (for a death or life-threatening event) **or 15 days** (for all other SAEs) **after the investigator's or institution's initial receipt of the information**. BMS will be provided with a simultaneous copy of all adverse events filed with the FDA. SAEs should be reported on MedWatch Form 3500A, which can be accessed at: <http://www.accessdata.fda.gov/scripts/medwatch/>.

**All SAEs should simultaneously be faxed or e-mailed to BMS at:**

**Global Pharmacovigilance & Epidemiology  
Bristol-Myers Squibb Company  
[contact]  
Email: [[contact]](mailto:[contact])**

Serious adverse events, whether related or unrelated to abatacept, must be recorded on the SAE page and reported within 24-hours to BMS (or designee) to comply with regulatory requirements. An SAE report should be completed for any event where doubt exists regarding its status of seriousness.

All SAEs must be reported within 24-hours by confirmed facsimile transmission (fax) and mailing of the completed SAE page. In some instances where a facsimile machine is not available, overnight express mail may be used. If only limited information is initially available, follow-up reports are required. (Note: Follow-up SAE reports should include the same investigator term(s) initially reported.) In selected circumstances, the protocol may specify conditions that require additional telephone reporting.

If the investigator believes that an SAE is not related to the investigational product but is potentially related to the conditions of the study (such as withdrawal of previous therapy, or a complication of a study procedure), the potential relationship should be specified in the narrative section of the SAE report.

If an ongoing SAE changes in its intensity or relationship to the investigational product, a follow-up SAE report should be sent within 24 hours to BMS. As follow-up information becomes available it should be sent within 24 hours using the same procedure used for transmitting the initial SAE report. All SAEs should be followed to resolution or stabilization.

### **7.3.2        *Handling of Expedited Safety Reports***

In accordance with local regulations, BMS will notify investigators of all SAEs that are suspected (related to the investigational product) and unexpected (ie, not previously described in the Investigator Brochure). In the European Union, an event meeting these criteria is termed a Suspected Unexpected Serious Adverse Reaction (SUSAR). BMS will send investigators an expedited safety report (ESR) to notify them of such an event.

Other important findings that BMS may report as ESRs include increased frequency of a clinically significant expected SAE, an SAE considered associated with study procedures that could modify the conduct of the study, lack of efficacy that poses significant hazard to study subjects, clinically significant safety findings from a nonclinical (eg, animal) study, important safety recommendations

from a study data monitoring committee, or the decision by BMS to end or temporarily halt a clinical study for safety reasons.

Upon receiving an ESR from BMS, the investigator must review and retain the ESR with the Investigator Brochure. Where required by local regulations or when there is a central IRB/IEC for the study, BMS will submit the ESR to the appropriate IRB/IEC. The investigator and IRB/IEC will determine if the informed consent requires revision. The investigator should also comply with the IRB/IEC procedures for reporting any other safety information.

In addition, BMS will report suspected serious adverse reactions (whether expected or unexpected) to the relevant health authorities in all concerned countries according to local regulations (either as expedited and/or in aggregate reports).

### **7.3.3        *Nonserious Adverse Events***

The investigator will begin collecting nonserious adverse event (NSAE) information once administration of the investigational product is initiated. This NSAE information should also be collected from the start of a placebo lead-in period or other observational period intended to establish a baseline status for the subjects.

All identified NSAEs must be recorded and described in the medical record. If an ongoing NSAE worsens in its intensity, or if its relationship to the investigational product changes, a new NSAE entry for the event should be completed. NSAEs should be followed to resolution or stabilization, or reported as SAEs if they become serious. Follow-up is also required for NSAEs that cause interruption or discontinuation of investigational product, or those that are present at the end of study participation. Subjects with NSAEs at study completion should receive post-treatment follow-up as appropriate.

### **7.4            *Laboratory Test Abnormalities***

All laboratory test results captured as part of the study should be recorded following institutional procedures. When reporting a test result that constitutes an adverse event, the clinical term should be used; for example, the event should be reported as “anemia” not “low hemoglobin.” Test results that constitute SAEs should be documented and reported as such.

### **7.5            *Overdose***

An overdose is defined as the accidental or intentional ingestion or infusion of any dose of a product that is considered both excessive and medically important. All occurrences of overdose must be reported as an SAE.

### **7.6            *Pregnancy***

Sexually active WOCBP must use an effective method of birth control during the course of the study, in such a manner that the risk of failure is minimized. (See Section 4.2.1 for the definition of WOCBP.) Before enrolling WOCBP in this study, investigators must review the BMS-provided information about study participation for WOCBP, which can also be found in the GCP Manual for Investigators. The topics include the following:

- General Information
- Informed Consent Form

- Pregnancy Prevention Information Sheet
- Drug Interactions with Hormonal Contraceptives
- Contraceptives in Current Use
- Guidelines for the Follow-up of a Reported Pregnancy.

Before study enrollment, WOCBP must be advised of the importance of avoiding pregnancy during study participation and of the potential risk factors for an unintentional pregnancy. The subject must sign an informed consent form documenting this discussion.

#### **7.6.1        *Requirements for Pregnancy Testing***

**All WOCBP MUST have a negative pregnancy test within 72 hours before receiving abatacept.** The minimum sensitivity of the pregnancy test must be 25 IU/L or equivalent units of HCG. If the pregnancy test is positive, the subject must not receive abatacept and must not continue in the study.

**In addition, all WOCBP must be instructed to contact the investigator and/or other study personnel immediately if they suspect they might be pregnant (eg, missed or late menstrual period) at any time during study participation.**

#### **7.6.2        *Reporting of Pregnancy***

If, following initiation of the investigational product, it is subsequently discovered that a study subject is pregnant or may have been pregnant at the time of investigational product exposure, including during at least 6 half-lives after administration, the investigational product will be permanently discontinued in an appropriate manner (eg, dose tapering if necessary for subject safety). The investigator must immediately notify BMS of this event and record the pregnancy on the Pregnancy Surveillance Form (not on an SAE form). Initial information on a pregnancy must be reported immediately to BMS, and information on the outcome provided once it is available. Completed Pregnancy Surveillance Forms must be forwarded to BMS according to SAE reporting procedures.

**Note:** Any pregnancy that occurs in a female partner of a male study subject must be reported to BMS using the Pregnancy Surveillance Form.

Protocol-required procedures for study discontinuation and follow-up must be performed for the subject unless contraindicated by pregnancy (eg, x-ray studies). Other appropriate pregnancy follow-up procedures should be considered if indicated. Information regarding the course of the pregnancy, including perinatal and neonatal outcome, must be reported to BMS on the Pregnancy Surveillance Form. Infants should be followed for a minimum of 8 weeks.

#### **7.7            *Other Safety Considerations***

Any significant worsening noted during interim or final physical examinations, electrocardiograms, x-rays, and any other potential safety assessments, whether or not these procedures are required by the protocol, should also be recorded in the medical record.

#### **7.8            *Safety Data Reconciliation***

The investigator will reconcile the clinical database SAE cases transmitted to BMS Global Pharmacovigilance (GPV&E). Frequency of reconciliation will be determined prior to study commencement but will occur no less than once prior to study database lock. BMS GPV&E will e-mail upon request from the investigator, the GPV&E reconciliation report. Requests for reconciliation should be sent to [[contact]](mailto:[contact]). The data elements listed on the GPV&E reconciliation report will be used for case identification purposes. If the investigator determines a case was not transmitted to BMS GPV&E, the case will be sent immediately.

## **8 STATISTICAL CONSIDERATIONS**

### **8.1 Sample Size Determination**

We based our sample sizes on the preliminary data (unpublished): SLE patients with arthritis at the start of a treatment had a mean score on 66-joint count of  $21 \pm 8.2$ . There was a decrease to a mean of  $2.0 \pm 1.5$  after 12 weeks of various interventions in patients who reported they improved. For the study proposed here, if 67% of abatacept pts will achieve 20% improvement in swollen and tender joints vs. 30% of controls by week 16, n=28 per group (with p=0.05, power=0.8). Thus we plan 32 patients for abatacept over 16 weeks and 32 patients for placebo over 16 weeks, a total of 64. The dropout rate in the abatacept non-nephritis lupus trial was 35% (over 12 months). We anticipate one-third that in a 4 month trial, proposed, here – i.e. 12%. If we begin with 64 patients we should have 56 completers, thus approximately 28 in each group.

Thus, we will plan to recruit 32 SLE patients at UCLA and an additional 32 at UCSD (separate contract).

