Study Design:	Randomized trial of 32 SLE patients treated with subcutaneous abatacept 125mg sq once a week vs. 32 placebo treated subjects over a 16 week period. Patients will be seen every 4 weeks from baseline. One half of patients will be recruited at UCLA and one-half at UCSD. We expect 30 patients in each group to complete the 16 week study.
Study Schema Drugs / Doses / Length of Treatment)	Abatacept 125 mg or placebo will be administered subcutaneously once a week for 16 weeks. There will be a telephone follow up 2 months after the last injection to capture post-treatment adverse events.
Accrual Goal: (Total number of subjects)	64 (32 at UCLA and 32 at UCSD)
Accrual Rate: (Number of subjects expected per month)	2-3 subjects per month at each site
FPFV: April 1, 2015 LPFV: March 31, 2018  Follow Up: 16 weeks per patient plus 8 weeks of observation for adverse events	
Correlative Studies: These will be performed at the UCLA site only	
1) Biomarkers: a) T cell numbers and phenotypic and functional characteristic in PBMC measured at week 0 and 16. These will include for T cells CD4+, CD3+, CD25+, CD8+, Foxp3+ and cytoplasmic stains for IFNgamma, IL2, IL-17, IL21 and IL-10.
 
b) B cell numbers and subsets, including naïve, activated and plasmablasts.
 
c) Ability of autologous CD4+CD25hi T cells to suppress proliferation of CD4+CD25- T cells.
 
d) Cytokines in serum: IFNgamma, IL-6, IL-10, IL-17, IL23 and BLyS
 
2) Ultrasound with power Doppler of joints assessing synovitis, tenosynovitis (18 joints) and erosions at week 0 and 16.

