### **8.2 Populations for Analyses**

The study analyses will be performed at the termination of the study; once the last visit of the last patients has been recorded. The analyses will be performed on the 64 SLE patients enrolled in the study based on the inclusion and exclusion criteria as stated above.

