### ***8.4.3 Efficacy Analyses***

The Fisher's exact test will be used to compare the percent of subjects achieving primary and secondary outcomes between two groups. Wilcoxon rank sum tests will be used to compare ordinal and quantitative outcomes between groups. Logistic regression will also be used to adjust for baseline clinical presentation and demographic factors. A site by treatment interaction effects will be included in the model to account for possible differences in treatment efficacy between our two sites. Bivariate analysis and nonparametric analysis (for example local polynomial regression or generalized additive model analysis) will be carried out to inspect the relationship between outcome and covariates. The goodness-of-fit of logistic models will be evaluated using the Hosmer-Lemeshow test. With the quantitative outcomes such as joint counts, ultrasound measurements, etc we will use Poisson regression to assess the treatment effect or linear regression for continuous outcomes. Poisson regression is a special case of generalized linear model and robust pseudo likelihood inference will be used in the analysis. We also will use multiple imputation technique to accommodate possible missing data at 12 and 24 weeks due to patients lost to follow up. The imputation model will include all baseline 12 week and 24 week outcomes and covariates to impute the missing outcomes . Analyses will be done with and without imputation.

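### The 80% power stated for 28 per group is not the power of Fisher's exact test, the planned primary test: two-sided, it is 71% at 28, 77% at 30 and 82% at 32 per group

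*Combined protocol and SAP*

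**What the plan says.** Section 8.1 assumes a response rate of 67% on abatacept and sets the comparison and the resulting size as "vs. 30% of controls by week 16, n=28 per group (with p=0.05, power=0.8"). It names neither the test behind this calculation nor the sidedness of the 0.05. It then plans 32 patients per group to allow for 12% dropout and concludes: "If we begin with 64 patients we should have 56 completers, thus approximately 28 in each group".

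The Synopsis (Study Design) gives a different completer number: "We expect 30 patients in each group to complete the 16 week study".

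Section 8.4.3 names the primary test: Fisher's "exact test will be used to compare the percent of subjects achieving primary and secondary outcomes between two groups". Logistic regression is described as an additional, adjusted analysis. On who is analysed, Section 8.2 says "The analyses will be performed on the 64 SLE patients enrolled in the study", and Section 8.4.3 adds "Analyses will be done with and without imputation".

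**The concern.** A power figure belongs to a particular test. At about 30 patients per arm, Fisher's exact test is clearly conservative: its real type I error lies well below the nominal 5%, and it loses power accordingly. A sample size from an uncorrected normal approximation therefore overstates the power of a trial that is analysed with Fisher's test.

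At stake is the main design claim of a 64-patient trial. If power at the expected number of completers is nearer 70–75% than 80%, the chance of missing the assumed effect is larger than the protocol says, and a non-significant result carries less weight against the drug than a reader of Section 8.1 would think. The two completer figures add to the problem, because it is unclear which evaluable number the power is meant to describe.

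**Working it through.** **Inputs.** Response rates 0.67 and 0.30, alpha 0.05, target power 0.80, 28 per group, 32 enrolled per group and 12% dropout are from Section 8.1. The 30 completers per group are from the Synopsis. Fisher's exact test is from Section 8.4.3. Two-sided testing is my assumption, since the documents do not say.

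**1. Reproducing the plan's 28.** The pooled, uncorrected formula is

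n = [z₀.₉₇₅·√(2p̄(1−p̄)) + z₀.₈₀·√(p₁(1−p₁) + p₂(1−p₂))]² / (p₁−p₂)²

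with p̄ = (0.67 + 0.30)/2 = 0.485 and p₁−p₂ = 0.37:

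n = [1.960 × 0.7068 + 0.8416 × 0.6566]² / 0.37² = 27.4, rounded up to 28.

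The nominal power of this formula at 28 is 80.8%. The arcsine formula gives 27.3, also 28. The continuity-corrected formula, which approximates Fisher's test, gives 33 (32.6 before rounding). So 28 is a correct figure for an uncorrected chi-square or z test.

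**2. Exact power of the planned test.** For n per group, list all pairs (x₁, x₂) with x₁ ~ Bin(n, 0.67) and x₂ ~ Bin(n, 0.30), compute the two-sided Fisher p-value of each table, and add the probabilities of the tables with p ≤ 0.05.

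| Evaluable per group | Two-sided Fisher power | Chance of missing the effect |
|---|---|---|
| 28 (Section 8.1) | 71.3% | 28.7% |
| 29 | 74.0% | 26.0% |
| 30 (Synopsis) | 76.8% | 23.2% |
| 31 | 79.3% | 20.7% |
| 32 (no missing outcomes) | 81.7% | 18.3% |

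The smallest equal group size that reaches 80% is 32. The maximum type I error at 28 per group, over a fine grid of common response rates, is 2.8%. That unused alpha is where the power goes. To reach 80% at 28 per group, the abatacept rate would have to be 70.4% rather than 67%.

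**3. Letting the number of completers vary.** Assume 32 randomised per arm and independent, equal dropout, and average Fisher power over Bin(32, 1−d) completers in each arm.
- d = 12% (Section 8.1): 75.3%.
- d = 2/32 = 6.25% (implied by 30 of 32 in the Synopsis): 79.5%.

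**4. Other readings.**
- One-sided 0.05: 80.4% at 28 per group. No passage states a one-sided test.
- All 64 analysed with dropouts counted as non-responders (an assumption; the protocol does not state it): the rates become 0.88 × 0.67 = 0.590 and 0.88 × 0.30 = 0.264 at 32 per group, and Fisher power is 70.1%.
- Boschloo's unconditional exact test, at the assumed rates: 79.7% at 28 (maximum type I error 4.6%), 82.7% at 30 and 83.0% at 32. With all 64 analysed and 12% dropouts as non-responders: 74.3%.

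**The case against.** **The 28 is not a miscalculation.** This stands. It reproduces under a standard formula, and Section 8.1 names no test. The fault is a mismatch between the sizing formula and the test in Section 8.4.3.

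**71.3% is a low point produced by exactly equal arms.** The power of a discrete test jumps with small imbalances: 74.5% with 27 on abatacept and 28 on placebo, 74.6% with 27 and 29, 77.0% with 28 and 29. Section 8.1 says approximately 28, so the 75.3% average describes the expected trial better. This is accurate and belongs in any restatement. It does not rescue the claim: 71.3% is the like-for-like value for 28 per group, and neither dropout average reaches 80%, although the Synopsis figure comes within half a point.

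**Section 8.2 analyses all 64 patients.** If every one of the 32 per group has an observed outcome at the assumed rates, power is 81.7% and the target is met. Some early leavers will supply data: the schedule includes a joint count at early withdrawal, and patients who fail the steroid or background-therapy rules are classed as failures. But Section 8.1 itself ties the power to 28 completers, multiple imputation does not recreate lost outcomes, one set of analyses is run without imputation, and the documents do not say how a dropout is scored for the primary endpoint. If dropouts count as non-responders, power falls to about 70%.

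**The test might be one-sided.** Then 28 would suffice. Nothing in the documents says so, and the silence is itself a gap.

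**No estimate or error rate is harmed.** True. This limits the seriousness but does not make the stated power correct.

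**Conclusion.** The concern holds. For a two-sided 5% Fisher's exact test at 67% versus 30%, power at 28 per group is 71.3%, about 9 points below the stated 80%. At the Synopsis figure of 30 per group it is 76.8%, about 3 points below. Allowing for random dropout, the expected shortfall is about 5 points at the 12% rate in Section 8.1 and about half a point at the rate that the Synopsis implies. The target is met only if all 32 per group are evaluable at the assumed rates (81.7%).

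The conclusion rests on two-sided testing and on the protocol's own response rates. It concerns an overstated design claim: there is no bias, and Fisher's test keeps type I error below 5%. Separately, 28 and 30 completers per group cannot both be the expectation. This should be fixed, and wording is enough.

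**What to change.** In Section 8.1, state that the test is two-sided (or otherwise), name the test that the power refers to, and give Fisher power at the expected evaluable number: about 71% at exactly 28 per group, 77% at 30, and 82% only if all 32 per group have an outcome. It is fair to add the averages over random dropout, 75% at 12% and 79.5% at 6.25%. Use one completer number in the Synopsis and Section 8.1.

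Optionally, and only before unblinding, name Boschloo's unconditional exact test for the primary comparison in Section 8.4.3. It gives 79.7% at 28 per group among completers, and about 74% if all 64 are analysed with 12% dropouts as non-responders.

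The cost is a few sentences and a less favourable stated power if Fisher's test is kept; the optional change of test adds one sentence and a different software call. No added enrolment is needed if the lower power is accepted and stated. Holding 80% for two-sided Fisher among completers would need 32 completers per group, that is 32/0.88 = 36.4, so 37 enrolled per group.
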